**EMERGENCY TELEPHONE NUMBERS**

## Protocol Change History

Version	Section(s)	Page(s)	Description of Change(s)	Rationale for Change(s)
1.0	N/A	N/A	Original	N/A
2.0	Sponsor Personnel	4	Added Medical Safety Officer	Updated sponsor personnel to include Medical Safety Officer
	1 Synopsis: Clinical Hypothesis	10	Changed the primary endpoint timepoint from 3-months to 1-week and specified that the requirement for preoperative astigmatism is corneal astigmatism	Updated to align with the planned timepoint for analysis for the primary endpoint and provided clarification preoperative astigmatism requirement.
	1 Synopsis: Number of Subjects; 8 Study Population	11, 19	Changed the timepoint for the target to achieve approximately 100 bilaterally-implanted subjects available for analysis from 3-months to 1-week. Number of subjects was changed from approximately 20 subjects to approximately 15 subjects.	Updated to align with the planned timepoint for analysis for the primary endpoint and the planned number of subjects to be enrolled per site.
	1 Synopsis: Evaluation Criteria	12	Added the word "the" in the first sentence and changed the primary endpoint timepoint from 3-months to 1-week	Grammatical change and updated to align with the planned timepoint for analysis for the primary endpoint
	1 Synopsis & 8.1 Inclusion Criteria	11, 19	Pre-existing corneal astigmatism of one diopter or greater;	Corrected error with the inclusion criteria
	1 Synopsis: Exclusion Criteria; 8.2 Exclusion Criteria	12, 20	Added planned monovision as an exclusion criterion.	To clarify the refractive requirements for the study.
	1 Synopsis: Data Analysis	12-13	Changed the primary endpoint timepoint from 3-months to 1-week. Provided clarification that the percent of eyes with misalignments will also be reported for all other postoperative timepoints (1-day and 3-months)	Updated to align with the planned timepoint for analysis for the primary endpoint and provided clarification for other endpoint data at other postoperative timepoints.
	5. Acronyms	14-15	Added ADE, BSS, UADE and USADE. Corrected spelling error for HIPAA.	ADE, BSS, UADE and USADE were missing from the list of Acronyms and the acronym for HIPAA was incorrect.
6 Study Objectives and Endpoints; 6.1 Primary Endpoint; 6.2 Other Endpoints	15-16	Changed the primary endpoint timepoint from 3-months to 1-week. Provided clarification that the 3-month visit will be the key timepoint for visual acuity, manifest refraction and patient and investigator reported outcomes questionnaire evaluations and that other timepoints will be provided as supportive analysis. Changed Percentage of eyes that achieve UCDVA of 0.3, 0.2, 0.1 & 0.0 logMAR to 20/40,	Updated to align with the planned timepoint for analysis for the primary endpoint and provided clarification for other endpoint data at other postoperative timepoints.	

Version	Section(s)	Page(s)	Description of Change(s)	Rationale for Change(s)
			20/32, 20/25 & 20/20. Changed Percentage of eyes with lens axis misalignments < 5° to ≤ 5°.	
2.0	7.1 Table 1 Intraocular lens	18	Table 1 revised	Table 1 revised to match DFU
	9.3 Investigator Approval	22-23	Deleted Clinical Investigator Brochure Signature Page and Hospital/Ambulatory Surgery Center Clinical Study Acknowledgement from the list of documents to be signed and returned to JJSV.	The Clinical Investigator Brochure is not a requirement for this study since the IOLs are marketed product. The Directions for Use is applicable for this study. Also removed Hospital/Ambulatory Surgery Center Clinical Study Acknowledgement to reflect current practice.
	10.1 Experimental Plan, Overview	23	Grammatical changes to 2 nd and 3 rd paragraph. Also deleted slit lamp from the procedures that will be done at the operative visit.	To correct grammatical changes and to reflect revised protocol requirements for procedures to be done at the operative visit.
	10.2 Visit Schedule	23	Deleted foot note “a” from the 3-month visit.	Foot note “a” was initially referenced at the 3-month visit in error. This deletion corrects the error.
	10.3 Preoperative Procedures	23-25	
 
Deleted Uncorrected Distance Visual Acuity from the procedures that should be done at the Preoperative Visit and provided clarification regarding additional preoperative information that should be collected.
 
 Made correction to IOL model (from ZCT to ZCU);	To correct typo in original version
	10.6 Operative Procedures	26-28	
 
Provided clarification regarding additional procedures that can't be performed during surgery. Also referenced Appendix for instructions for capturing photographs through the surgical microscope.
 
 Implant Instrument Used – added implant instruments that are approved to be used in the study. Specified that BSS will be collected on the case report form.	Some of the implant instruments that are approved for use in the study were inadvertently not included in Version 1.0 of the protocol. Also clarified that BSS solution used will be recorded in the case report form.
	10.7 Postoperative Procedures	29-31	
 
Provided clarification regarding postoperative procedures for uncorrected distance visual acuity testing, manifest refraction, best corrected distance visual acuity and biomicroscopic slit lamp photographs and lens axis orientation.
 
Provided clarification regarding training requirements for individuals performing slit lamp exams and photography.
 
	To provide clarity for the testing requirements for uncorrected distance visual acuity, best corrected distance visual acuity and manifest refraction at the postoperative visits.

Version	Section(s)	Page(s)	Description of Change(s)	Rationale for Change(s)
			
 
Added the requirement for the Investigator Satisfaction Questionnaire to be completed at the 1-week visit.
 
Updated letters for the Appendix references to reflect the updated appendices.
 
Added details regarding handling secondary surgical interventions in the study
 
 
Added details regarding the use of M&S System for uncorrected distance visual acuity, best corrected distance visual acuity and manifest refraction testing.
	
2.0	10.8 Exit of Subjects	32	
 
Added slit lamp photographs of IOL position to the list of data that may be collected at an unscheduled visit. Also, clarified that fundus exam can be dilated or undilated.
 
Provided clarification regarding the procedures that are required to be completed if a greater degree of rotation is noted since last study visit and IOL repositioning is required.
 
 
Clarified instructions for handling surgical complications and discontinued subjects.
	To clarify subject exit procedures and requirements.
	10.9 Unscheduled Visits	33	
 
Added slit lamp photographs of IOL position to the list of data that may be collected at an unscheduled visit. Also, clarified that fundus exam can be dilated or undilated.
 
Provided clarification regarding the procedures that are required to be completed if lens axis orientation had changed since last study visit and IOL repositioning is required.
 
 
Updated the method of estimating the amount of rotation and clarified requirements for completing an unscheduled visit for a second eye 1-day or 1-week visit if the first eye is examined.
	To provide clarity regarding the requirements for estimating the amount of rotation and completion of unscheduled visits for a second eye 1-day or 1-week visit if the first eye is examined.
	10.10 Protocol Deviations	33	Updated to reflect that protocol deviations will be documented in the Clinical Trial Management System.	Corrected to reflect the planned process for handling protocol deviations.
	11.1 Adverse Event Definitions	34	Updated letters for the Appendix references to reflect the updated appendices.	To provide the correct Appendix references.

Version	Section(s)	Page(s)	Description of Change(s)	Rationale for Change(s)
2.0	23 Statistical Methods	43-45	Updated the timepoint for the rotational stability endpoint and specified that the 3-month timepoint is the key timeframe for other endpoints.	Updated to align with the planned timepoint for analysis for the primary endpoint and provided clarification for other endpoint data at other postoperative timepoints.
	23.1 Analysis Population	44	Provided clarification regarding the analysis population and available axis data. Also provided clarification on how data will be handled if a repositioning or lens removal procedure is required.	To provide clarity regarding the analysis population and situational data.
	23.2 Primary study endpoint	44	Updated the timepoint from 3-months to 1-week for the primary endpoint	Updated to align with the planned timepoint for analysis for the primary endpoint
	23.3 Other Endpoint	45	Updated to reflect the revised timeframes for other endpoint data.	Updated to align with the planned timepoint for analysis for the other endpoint data
	Appendix A	46	Updated to reflect that pupil size will be collected at all postoperative visits, complications/adverse events will also be collected at preoperative visits, and the Investigator Satisfaction Questionnaire will be completed at the 1-week visit.	Updated to align with study procedures per the revised protocol.
	Appendix B	47	Equipment list. This appendix was formerly Slit Lamp Exam Ratings.	Added to provide clarity regarding study equipment.
	Appendix C	48	Instructions for capturing photos through the surgical microscope. This appendix was formerly Slit Lamp Retroillumination Photographs.	Added to provide instructions for capturing photographs through the surgical microscope.
	Appendix D	49	Instructions for Using the M&S System. This appendix was formerly American Academy of Ophthalmology Task Force Consensus Statement on Adverse Events for Intraocular Lenses	Added to provide instructions for using the M&S System.
	Appendix E	50	Instructions for Distance Visual Acuity Testing. This appendix was formerly Instructions for adverse event and complaint reporting	Added to provide instructions for performing distance visual acuity testing.
	Appendix F	51	Maximum Plus Manifest Refraction Technique with Cylinder Refinement. This appendix was formerly Patient Satisfaction Questionnaire (PSQ)	Added to provide instructions for maximum plus manifest refraction technique with cylinder refinement
Appendix G	52	Refraction Adjustments. This appendix was formerly Investigator Satisfaction Questionnaire (ISQ)	Added to provide instructions for refraction adjustments.	

Version	Section(s)	Page(s)	Description of Change(s)	Rationale for Change(s)
2.0	Appendix J	57	Instructions for Lens Axis Measurement with Slit Lamp Updated appendix letter to reflect the appendix number in this revision of the protocol and updated the process for axis measurement.	Simplified the instructions for axis measurement estimation.
	Appendix B, C, D, E, F, G, H, I, J, K, L, M, N	47-61	Updated letters of each appendix to reflect additional appendices.	To provide the correct Appendix letters in order.
3.0	Sponsor Personnel	4	Added Head of Global Clinical Science; updated title for Director, Clinical Operations, Surgical Vision	Updated sponsor personnel to include Head of Global Clinical Science and to clarify title for Director, Clinical Operations, Surgical Vision
	1 Synopsis: Overall Study Design	13	Updated number of sites to up to 8 sites; clarified that refractive target outcomes will be emmetropia for each eye enrolled in the study; updated visit schedule to address either bilateral or unilateral subjects.	Updated to align with the study design change to allow for unilateral or bilateral enrollment.
	1 Synopsis: Study Population Characteristics	14-15	Updated to allow for unilateral or bilateral enrollment in the study; updated the total number of subjects to be enrolled in the study, percentage of eyes from unilateral and bilateral subjects, and the expected number of subjects per site; updated the inclusion criteria to allow for unilateral or bilateral enrollment; updated the exclusion criteria to exclude enrollment of eye designated for near correction in subjects with planned monovision correction.	Updated to align with the study design change to allow for unilateral or bilateral enrollment.
	1 Synopsis: Study Visits and Procedures	16	Included clarification that the ICF will include designation as to whether one or both eyes are to be included in the study; clarifies that PSQ is only for bilaterally implanted subjects.	Updated to align with the study design change to allow for unilateral or bilateral enrollment.
	4 Study Design	17	Updated number of sites and total number of subjects to be enrolled in the study for unilateral or bilateral cataract surgery.	Updated to align with the study design change to allow for unilateral or bilateral enrollment.
	6.2 Other Endpoints	19	Clarifying that PSQ is only administered to bilateral subjects.	Updated procedures due to study design change.
	8 Study Population	22	Updated number of sites, total number of subjects to be enrolled in the study, percentage of eyes from unilateral and bilateral subjects, and the expected number of subjects per site; updated that subjects will be included for unilateral or bilateral cataract surgery.	Updated to align with the study design change to allow for unilateral or bilateral enrollment.

Version	Section(s)	Page(s)	Description of Change(s)	Rationale for Change(s)
3.0	8.1 Inclusion Criteria	23	Updated to allow for unilateral or bilateral enrollment	Updated to align with the study design change to allow for unilateral or bilateral enrollment.
	8.2 Exclusion Criteria	24	Updated to exclude enrollment of eye designated for near correction in subjects with planned monovision correction.	Updated to align with the study design change to allow for unilateral or bilateral enrollment.
	10.1 Experimental Plan Overview	26-27	Updated number of sites and total number of subjects to be enrolled in the study for unilateral or bilateral cataract surgery; percentage of eyes from unilateral and bilateral subjects; corrected the analysis time point to 1-week; clarified that PSQ is only administered to bilateral subjects.	Updated to align with the study design change to allow for unilateral or bilateral enrollment.
	10.2 Visit Schedule	27-28	Updated to account for bilateral or unilateral subjects: for bilateral subjects, 3-month visit window is based on the 2 nd eye operative date; added footnote to Table 2 to clarify instructions on bilateral 3-month visit.	Updated to align with the study design change to allow for unilateral or bilateral enrollment.
	10.3 Preoperative Procedures	29-30	Clarifying that preoperative procedures are to be performed for each enrolled eye; removed restriction for monovision.	Updated to align with the study design change to allow for unilateral or bilateral enrollment.
	10.6 Operative Procedures	30	Updated to allow for MIGS (minimally invasive glaucoma surgery) following consultation with the medical monitor.	Allowing for more standard of care procedures to be done with consultation with medical monitor.
	10.7 Postoperative Procedures	33, 35	Clarifying that Binocular UCDVA should be done for bilateral subjects only; clarifying that PSQ is only administered to bilateral subjects.	Updated to align with the study design change to allow for unilateral or bilateral enrollment.
	21 Statistical Methods	47	Adding that data from other study visits other than key timeframe may be reported for supportive analysis.	Updated to align with the study design change to allow for unilateral or bilateral enrollment.
	21.1 Analysis Population	48	Updated analysis to reflect changes due to unilateral or bilateral enrollment.	Updated to align with the study design change to allow for unilateral or bilateral enrollment.
	21.5 Sample Size calculation	49	Updated text to reflect sample size was calculated for 1-week instead of 3-months.	Updated to align with time frame for primary endpoint.
Appendix A	50	Updated footnotes to specify which procedures are applicable only in subjects bilaterally implanted with the study lens (binocular UCDVA and PSQ).	Updated to align with the study design change to allow for unilateral or bilateral enrollment.	

Version	Section(s)	Page(s)	Description of Change(s)	Rationale for Change(s)
	Appendix B	51	Updated equipment list to allow for a loan of a slit lamp compatible with slit-lamp camera.	To reflect current sites' equipment needs.
3.0	Appendix F	55	Removed Snellen and added M&S System to study Manifest Refraction procedure instructions.	Correction to procedure instructions as M&S System will be utilized to collect study Manifest Refraction.
	Appendix J	61	Updated instructions for lens axis measurement with slit lamp to use the limbus as a reference mark rather than the pupil.	Correction made to align with practical methods used by sites as pupil sizes may not be equal between each eye.

## 1. SYNOPSIS

**PROTOCOL:** Clinical Investigation of Rotational Stability of the TECNIS® Toric II Intraocular Lens

Protocol Number: NXGT-202-QROS

**STUDY LENS:** TECNIS Toric II – One-Piece Aspheric Acrylic Monofocal Posterior Chamber IOL (Model ZCU).

**STUDY OBJECTIVE:** The purpose of this clinical study is to evaluate the rotational stability of the TECNIS Toric II IOL.

**CLINICAL HYPOTHESIS:** TECNIS Toric II IOL will demonstrate excellent rotational stability by demonstrating  $\leq 5^\circ$  of axis misalignment from the intended IOL axis of orientation in 90% of eyes at the 1-week postoperative visit, in patients with preoperative corneal astigmatism.

### OVERALL STUDY DESIGN:

**Structure:** Prospective, multi-center, single-arm, open-label

**Number of sites:** Up to 8 sites

**Duration:** Three months

**Indication:** The TECNIS Toric II 1-Piece posterior chamber lenses are indicated for the visual correction of aphakia and pre-existing corneal astigmatism of one diopter or greater in adult patients with or without presbyopia in whom a cataractous lens has been removed by phacoemulsification and who desire improved uncorrected distance vision, reduction in residual refractive cylinder, and increased spectacle independence for distance vision. The device is intended to be placed in the capsular bag.

**Administration:** Refractive target outcomes will be emmetropia for each eye enrolled in the study. Surgeons will perform standardized, small-incision, cataract surgery and implant the study lenses using a JJSV-validated insertion system qualified for use with TECNIS Toric II lenses as specified in the Directions for Use (DFU).

**Visit Schedule:** Subjects will be implanted with the study lens in one or both eyes; in bilateral subjects the second eye is to be implanted within one-month of the first eye surgery. All eyes of all subjects will undergo a minimum of 5 to a maximum of 8 scheduled visits: Preoperative for both eyes; Operative each eye, 1-day each eye, and 1-week visits for each eye; and a 3-month visit for one or both eyes.

**STUDY POPULATION CHARACTERISTICS:**

**Condition:** Unilateral or bilateral cataracts with corneal astigmatism of approximately 1.0 D to 6.0 D.

Models ZCU 1.50, 2.25, 3.00, 3.75, 4.50, 5.25, 6.00

**Number of Subjects:** Up to 192 subjects will be enrolled to achieve 200 evaluable eyes at the 1-week visit with a target of 75% of the eyes coming from bilateral subjects and 25% of the eyes coming from unilateral subjects.

Each site should enroll approximately 24 subjects and no site may enroll more than 25% of the enrollment total.

**Inclusion Criteria**

1. Minimum 22 years of age;
2. Unilateral or Bilateral cataracts for which cataract extraction and posterior chamber IOL implantation have been planned;
3. Pre-existing corneal astigmatism of one diopter or greater;
4. Predicted residual refractive cylinder based on toric IOL calculator, considering surgically induced astigmatism (SIA) and posterior corneal astigmatism (PCA) must be  $\leq 0.50$  D;
5. Potential for postoperative BCDVA of 20/30 Snellen or better;
6. Clear intraocular media other than cataract in each eye;
7. Availability, willingness and sufficient cognitive awareness to comply with examination procedures and study visits;
8. Signed informed consent form (ICF) and health insurance portability and accountability act (HIPAA) authorization;
9. Ability to understand and respond to a questionnaire in English.

**Exclusion Criteria:**

1. Irregular corneal astigmatism;
2. Any corneal pathology/abnormality other than regular corneal astigmatism or corneal instability due to contact lens wear;
3. Previous corneal or intraocular surgery;
4. Inability to focus or fixate for prolonged periods of time (e.g., due to strabismus, nystagmus, etc.);
5. Any pupil abnormalities (non-reactive, fixed, or abnormally shaped pupils);
6. Dilated pupil size of  $< 6.0$  mm;

7. Recurrent severe anterior or posterior segment inflammation or uveitis;
8. Subjects with conditions associated with increased risk of zonular rupture, including capsular or zonular abnormalities that may lead to IOL decentration, including pseudoexfoliation, trauma, or posterior capsule defects;
9. Known ocular or systemic disease that, in the opinion of the investigator, may affect visual acuity or require surgical intervention during the course of the study, [macular degeneration, cystoid macular edema, proliferative diabetic retinopathy (severe), uncontrolled glaucoma, irregular corneal astigmatism, choroidal hemorrhage, concomitant severe eye disease, extremely shallow anterior chamber, microphthalmos, non-age related cataract, severe corneal dystrophy, severe optic nerve atrophy, etc.];
10. Use of systemic or ocular medications (e.g., Flomax) that may affect vision including prior, current, or anticipated use during the course of the study that may, in the opinion of the investigator, confound the outcome or increase the risk to the subject (e.g., poor dilation or a lack of adequate iris structure to perform standard cataract surgery);
11. Patient is pregnant, plans to become pregnant, is lactating or has another condition associated with the fluctuation of hormones that could lead to refractive changes;
12. Concurrent participation or participation within 30 days prior to the preoperative visit in any other clinical study.
13. Planned monovision correction (eye designated for near correction)

**NOTE:** *Physicians considering enrolling a patient with one or more of the conditions listed under the warning or precaution in the final approved labeling of the device should weigh the potential risk/benefit ratio before enrollment.*

#### **EVALUATION CRITERIA:**

The purpose of this clinical study is to evaluate the rotational stability of the TECNIS® Toric II IOL. Rotational stability of the IOL will be evaluated by measuring axis misalignment, which is defined as the absolute difference between intended IOL axis of orientation (immediately at the end of the surgery) and follow-up visit(s) as measured by a photographic based method.

#### **PRIMARY ENDPOINT**

The primary outcome for the study is the percentage of eyes with  $\leq 5^\circ$  axis misalignment from the intended IOL axis of orientation at the 1-week visit.

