### 3. CLINICAL HYPOTHESIS

TECNIS Toric II IOL will demonstrate excellent rotational stability by demonstrating  $\leq 5^\circ$  of axis misalignment from the intended IOL axis of orientation in 90% of the eyes at the 1-week postoperative visit.

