### 6.2 OTHER ENDPOINTS

- Residual mean manifest cylinder and spherical equivalent for all eyes
- Percentage of eyes that achieve UCDVA of 20/40, 20/32, 20/25 & 20/20
- Percentage of eyes that achieve accuracy of cylinder (to target):
  - within:  $\pm 0.50$  D and  $\pm 1.00$  D
- Analysis of lens axis misalignment (compared to target) including:
  - Mean absolute and signed value of the misalignment
  - Percentage of eyes with lens axis misalignments  $\leq 5^\circ$ ,  $< 10^\circ$ ,  $< 20^\circ$  and  $>30^\circ$
- Medical findings/Lens findings/Complications
- Subject responses on Patient Satisfaction Questionnaire (PSQ)

**NOTE:** Should be administered only in subjects who have been implanted with the study lens bilaterally

- Investigator responses on Investigator Satisfaction Questionnaire (ISQ)
- Adverse event rates including the rate of IOL repositioning and/or IOL exchange primarily due to IOL misalignment.

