**10.5 SELECTION OF THE IOL**

In order to facilitate IOL selection and axis placement, JJSV provides a web-based proprietary tool, the TECNIS Toric Calculator ([www.TecnisToricCalc.com](http://www.TecnisToricCalc.com)) for the surgeon. Preoperative keratometry, biometry data, incision location, spherical equivalent IOL power, and the surgeon's estimated surgically induced corneal astigmatism are used as inputs for the TECNIS Toric Calculator. These inputs are used to determine the axis of placement in the eye and the predicted residual refractive astigmatism for TECNIS Toric II 1-Piece IOL models.

**NOTE:** *The TECNIS Toric Calculator also provides an option for including the Posterior Corneal Astigmatism (PCA). The predetermined value for posterior corneal astigmatism must be included in the calculation by checking the box labeled "Include Posterior Corneal Astigmatism (PCA)".*

*Surgeons can use their preferred Toric Calculator for determination of lens axis placement.*

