## 21.2 PRIMARY ENDPOINT

### PROPORTION OF EYES WITHIN 5 DEGREES OF ABSOLUTE IOL ROTATION

The primary endpoint for this study is the amount of absolute axis rotation from operative axis to the 1-week visit as measured by the photographic axis method. The proportion of eyes with less than or equal to 5 degrees of absolute rotation at 1-week will be reported along with the 95% confidence interval for this proportion.

The clinical success criterion will be that 90% of eyes will have lens rotation of 5 degrees or less at 1-week using the photographic measurement method.

The primary study endpoint is based on objective analysis of study photographs by designated sponsor personnel.

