## 21.3 OTHER ENDPOINTS

### **Rotational Stability**

In addition to the absolute axis rotation at 1-week, data will also be reported at 1 day and 3 months. The proportion of eyes within 5° for all postoperative visits as well as the proportion of eyes with less than 10°, 20° and greater than 30° of rotation will be reported. Mean absolute rotation will also be reported for all visits using descriptive statistics.

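### Does wording the primary endpoint as misalignment from the intended axis, with an untimed back-up baseline photograph, put the rotation result in doubt?

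*Combined protocol and SAP*

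**What the plan says.** The synopsis (Primary Endpoint) counts eyes with at most 5° "axis misalignment from the intended IOL axis of orientation at the 1-week visit". Section 3 states the hypothesis as at most 5° "of axis misalignment from the intended IOL axis of orientation in 90% of the eyes at the 1-week postoperative visit". Neither sentence says what the intended axis is.

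The definition appears in the synopsis (Evaluation Criteria, repeated under Data Analysis) and in Section 6.1. Misalignment is the "absolute difference between intended IOL axis of orientation (immediately at the end of the surgery) and follow-up visit(s", measured from photographs. Section 21.2 uses different words: "The primary endpoint for this study is the amount of absolute axis rotation from operative axis to the 1-week visit". It sets success at 90% of eyes. Section 10.6 makes the end-of-case microscope photographs the baseline for later rotation measurements, and Appendix I measures rotation from the operative photograph.

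A planned axis also exists. Section 10.5 says of the toric calculator's inputs: "These inputs are used to determine the axis of placement in the eye".

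Section 6.2 lists, among the other endpoints, "Analysis of lens axis misalignment (compared to target) including", followed by "Mean absolute and signed value of the misalignment" and the share of eyes in bands at 5°, 10°, 20° and 30°. Section 21.3 says "Mean absolute rotation will also be reported for all visits using descriptive statistics" and does not mention a signed value.

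Where no high-quality image can be obtained at the end of surgery, Section 10.6 asks for a slit-lamp photograph after surgery as a back-up. Appendix A marks this in the operative column. Its footnote b also allows a slit-lamp photograph at the investigator's discretion.

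**The concern.** Three things look loose in a study whose only primary measure is change from a baseline image.

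- **Reference axis.** Section 10.6 (additional operative information) uses the word intended for planned values of spherical equivalent and cylinder. A reader could take the intended axis as the planned one too, and read a success as proof of placement to plan, which the study does not test.
- **Target in Section 6.2.** The term is not defined for axis, no sign convention is given, and the signed mean is missing from Section 21.3. The planned axis is not named in the protocol's data lists.
- **Back-up baseline.** No clock time is set, and the operative data list asks only for confirmation that photographs were taken and uploaded. Rotation before a late baseline is lost. Unless the lens turns back, that raises the observed success proportion.

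**Working it through.** **1. Which axis is the reference?** Set side by side, the sections agree:

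- Synopsis (Evaluation Criteria, Data Analysis) and Section 6.1: the intended axis is the one at the end of surgery.
- Section 10.6: the baseline is the end-of-case photograph.
- Section 21.2: rotation is measured from the operative axis.
- Appendix I: rotation is measured from the operative photograph.

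The sentences without the explanation do not stand alone. The synopsis endpoint directly follows Evaluation Criteria, and the opening of Section 6 is followed by Section 6.1. The hypothesis itself is framed as rotational stability. No section computes the primary endpoint from the calculator's axis.

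**2. What is the target in Section 6.2?** Its bands (≤5°, <10°, <20°, >30°) recur in the synopsis under the end-of-surgery definition, and in Section 21.3 under the name rotation. The natural reading is therefore rotation from the operative axis. Section 21 says that it highlights analyses of key endpoints, and it gives default summaries for continuous data. A signed mean listed in Section 6.2 can be produced under those defaults.

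**3. The plan's own precision (Section 21.5).** Inputs: 200 eyes, expected proportion 95%, two-sided 95% interval, eyes treated as independent.

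1.96 × √(0.95 × 0.05 / 200) = 0.0302, or 3.02 points. The stated 3.0 is reproduced.

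**4. Size of the back-up baseline effect.** Let p be the true proportion within 5°, f the share of eyes with a back-up baseline, and g the share of failing rotations in those eyes that occur before the photograph. If back-up eyes fail as often as others and lenses do not turn back:

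observed proportion = p + f × (1 − p) × g

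The documents give neither f nor g, so both are assumed over a range. The upward bias, in percentage points, is:

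| p | g | f = 5% | f = 10% | f = 20% |
|---|---|---|---|---|
| 95% | 1 | 0.25 | 0.5 | 1.0 |
| 95% | 0.5 | 0.125 | 0.25 | 0.5 |
| 90% | 1 | 0.5 | 1.0 | 2.0 |
| 90% | 0.5 | 0.25 | 0.5 | 1.0 |

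At the planning value the largest entry is 1.0 point, about a third of the 3.02-point half-width.

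**5. How many back-ups would move a failing lens to 90%?** With g = 1:

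- True 89%: f = 0.01 / 0.11 = 9.1%, or 18.2 of 200, so 19 eyes.
- True 88%: f = 0.02 / 0.12 = 16.7%, or 33.3 of 200, so 34 eyes.

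**6. What if the planned axis were used?** Assume normal, zero-mean, independent errors. Having 95% of eyes within 5° implies a rotation SD of 5 / 1.96 = 2.55°. Adding a placement-error SD of 2° gives √(2.55² + 2²) = 3.24°, and 87.7% of eyes within 5°. For SDs of 1° and 3° the figures are 93.2% and 79.6%. These placement errors are assumptions, and they describe an endpoint that the study does not use.

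**The case for a change.** The best case for a change is that the synopsis and hypothesis sentences are the ones most likely to be lifted into a report. Step 6 shows that the two readings can fall on opposite sides of 90%. Section 6.1 defines an absolute difference, so it cannot supply a sign convention for Section 6.2. The protocol lists neither the type nor the time of the baseline photograph, so it does not itself provide for showing that back-ups were rare. Back-up eyes might also fail more often than the rest, in which case the bias would exceed the figures in step 4.

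Part of this stands. The terms are uneven, the sign convention is missing, and the time of a back-up photograph is not a listed item. The risk of misreading is small, though, because the definition sits next to the endpoint sentences and Section 21.2 states the quantity plainly.

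On the back-up, Appendix A places the photograph at the operative visit, apart from the 1-day visit, which Section 10.2 sets at 1–2 days. Section 10.6 makes it a baseline only when an adequate image cannot be had. It also asks for at least three microscope photographs, and for video of the surgery where available. Footnote b permits a discretionary slit-lamp photograph but does not say that it replaces an adequate microscope baseline. For g = 1, every failing rotation in back-up eyes would have to occur before an operative-visit photograph, and nothing in the documents suggests that.

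**Conclusion.** The concern does not call for a change. The primary endpoint has one workable meaning, absolute rotation from the end-of-surgery photograph, and the uneven wording leaves its value unaffected. The Section 6.2 gap concerns a descriptive, non-primary summary. An analyst would fill it by taking the operative axis as reference and stating which direction is positive. A planned-axis analysis would go beyond the stated objective of rotational stability.

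The back-up baseline is a real but small source of optimism: at most 0.25 to 1.0 point at 95% for back-up shares of 5% to 20%, and at most 0.5 to 2.0 points at 90%. These bounds assume that back-up eyes fail at the same rate as others and that lenses do not turn back; the shares themselves are assumed. Only frequent back-ups together with a true proportion just under 90% could affect the success criterion. Reporting how many eyes used a back-up would be good documentation. It would not alter what the trial does or can conclude.
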